Appendix VII EORTC QLQ CIPN-20 Instrument

EORTC QLQ – CIPN20

Patients sometimes report that they have the following symptoms or problems. Please indicate the extent to which you have experienced these symptoms or problems during the past week. Please answer by circling the number that best applies to you.

During the past week:

	Not at All	A Little	Quite a Bit	Very Much
31 Did you have tingling fingers or hands?	1	2	3	4
32 Did you have tingling toes or feet?	1	2	3	4
33 Did you have numbness in your fingers or hands?	1	2	3	4
34 Did you have numbness in your toes or feet?	1	2	3	4
35 Did you have shooting or burning pain in your fingers or hands?	1	2	3	4
36 Did you have shooting or burning pain in your toes or feet?	1	2	3	4
37 Did you have cramps in your hands?	1	2	3	4
38 Did you have cramps in your feet?	1	2	3	4
39 Did you have problems standing or walking because of difficulty feeling the ground under your feet?	1	2	3	4
40 Did you have difficulty distinguishing between hot and cold water?	1	2	3	4
41 Did you have a problem holding a pen, which made writing more difficult?	1	2	3	4
42 Did you have difficulty manipulating small objects with your fingers (for example, fastening small buttons)?	1	2	3	4
43 Did you have difficulty opening a jar or bottle because of weakness in your hands?	1	2	3	4
44 Did you have difficulty walking because your feet dropped downwards?	1	2	3	4

Please go on to the next page

During the past week:

	Not at All	A Little	Quite a Bit	Very Much
45 Did you have difficulty climbing stairs or getting up out of a chair because of weakness in your legs?	1	2	3	4
46 Were you dizzy when standing up from a sitting or lying position?	1	2	3	4
47 Did you have blurred vision?	1	2	3	4
48 Did you have difficulty hearing?	1	2	3	4

Please answer the following question only if you drive a car

49 Did you have difficulty using the pedals?	1	2	3	4
--	---	---	---	---

Please answer the following question only if you are a man

50 Did you have difficulty getting or maintaining an erection?	1	2	3	4
--	---	---	---	---

Appendix VIII Patient Analgesic Use Questionnaire

Initials _____
Study # _____
Date _____
Day _____

Please list all pain medications (drug, dose, and quantity) used in the past 24 hours.

Drug	Unit Dose	Quantity over past 24 hours
Example Acetaminophen or Tylenol	500 mg	4 pills

Appendix IXA Global Impression of Change and Patient Preference Questionnaire – Upper Extremity

**SUBJECT GLOBAL IMPRESSION OF CHANGE – NEUROPATHY
(Upper Extremity)**

Initials	_____
Study #	_____
Date	_____
Day	_____

1. Since beginning the study treatment, my fingers or hands neuropathy symptoms are:

-3	-2	-1	0	+1	+2	+3
very much	moderately	a little	about the	a little	moderately	very much
worse	worse	worse	same	better	better	better

2. Since beginning the study treatment, my finger or hand pain is:

-3	-2	-1	0	+1	+2	+3
very much	moderately	a little	about the	a little	moderately	very much
worse	worse	worse	same	better	better	better

3. Since beginning the study treatment, my overall quality of life is:

-3	-2	-1	0	+1	+2	+3
very much	moderately	a little	about the	a little	moderately	very much
worse	worse	worse	same	better	better	better

Would you recommend this therapy to other patients with problems similar to yours?

- No
- Yes
- Unsure

Comments:

Appendix IXB Global Impression of Change and Patient Preference Questionnaire – Lower Extremity

SUBJECT GLOBAL IMPRESSION OF CHANGE – NEUROPATHY (Lower Extremity)

Initials _____
Study # _____
Date _____
Day _____

1. Since beginning the study treatment, my toes or feet neuropathy symptoms are:

-3	-2	-1	0	+1	+2	+3
very much worse	moderately worse	a little worse	about the same	a little better	moderately better	very much better

2. Since beginning the study treatment, my toe or foot pain is:

-3	-2	-1	0	+1	+2	+3
very much worse	moderately worse	a little worse	about the same	a little better	moderately better	very much better

3. Since beginning the study treatment, my overall quality of life is:

-3	-2	-1	0	+1	+2	+3
very much worse	moderately worse	a little worse	about the same	a little better	moderately better	very much better

Would you recommend this therapy to other patients with problems similar to yours?

- No
- Yes
- Unsure

Comments:

Appendix XA Daily Scrambler Treatment Log and Adverse Event Assessment

Patient Name: _____

Date: _____

Initials	_____
Study #	_____
Date	_____
Day	_____

Pain Area #1 _____

VAS Score: Pre: _____ During: _____ Post: _____

Cable 1	Max Setting: _____	Total Treatment Time: _____ (mins)
Cable 2	Max Setting: _____	Total Treatment Time: _____ (mins)
Cable 3	Max Setting: _____	Total Treatment Time: _____ (mins)
Cable 4	Max Setting: _____	Total Treatment Time: _____ (mins)
Cable 5	Max Setting: _____	Total Treatment Time: _____ (mins)

Pain Area #2 _____

VAS Score: Pre: _____ During: _____ Post: _____

Cable 1	Max Setting: _____	Total Treatment Time: _____ (mins)
Cable 2	Max Setting: _____	Total Treatment Time: _____ (mins)
Cable 3	Max Setting: _____	Total Treatment Time: _____ (mins)
Cable 4	Max Setting: _____	Total Treatment Time: _____ (mins)
Cable 5	Max Setting: _____	Total Treatment Time: _____ (mins)

Adverse Effects Assessment: Please note any toxicities/adverse effects of treatment

Notes/Comments:

Appendix XB Daily TENS Treatment Log and Adverse Event Assessment

Initials _____
Study # _____
Date _____
Day _____

Patient Name: _____

Pain Area #1 _____

Cable 1 Max Setting: _____

Total Treatment Time: _____ (mins)

Pain Area #2 _____

Cable 2 Max Setting: _____

[figure not shown]
[figure not shown]
Total Treatment Time: _____ (mins)

Adverse Effect Assessment: Please note any adverse effects of treatment

Notes/Comments:

Appendix XI Individual Patient Dermatome Map
(page 1)

Initials	_____
Study #	_____
Date	_____
Day	_____

[figure not shown]

Appendix XI Individual Patient Dermatome Map (page 2)

Indicate:
Pain with "P"
Numbness with "N"
Tingling with "T"

Electrode placement
indicated with circle

Initials _____
Study # _____
Date _____
Day _____

7. How much of a problem has **pain** in your fingers or hands been **in the past week**?

0	1	2	3	4	5	6	7	8	9	10
No pain in fingers and/or hands										Pain in fingers and/or hands as bad as you can imagine

8. How much **pain**, have you had in your fingers or hands **at its worst over the past 24 hours** (circle one number)?

0	1	2	3	4	5	6	7	8	9	10
None										As bad as can be

9. How much **pain**, have you had in your fingers or hands **on average over the past 24 hours** (circle one number)?

0	1	2	3	4	5	6	7	8	9	10
None										As bad as can be

10. Which is the most problematic symptom that you have now (**over the past day**)?

Numbness

Tingling

Burning/shooting pain

Other, please indicate _____

Appendix XIIB Patient Weekly Follow-up Questionnaire for Lower Extremity Neuropathy

Initials _____
Study # _____
Date _____
Day _____

Everyone has aches and pains at some time. We are interested in your experience of numbness, tingling and pain that you have developed related to chemotherapy. Please address these questions related to this.

Directions: Please answer the following questions about your symptoms

1. How much of a problem has **numbness** in your toes or feet been **in the past week**?

0	1	2	3	4	5	6	7	8	9	10
No										Numbness in
numbness in										toes and/or feet
toes and/or										as bad as you
feet										can imagine

2. How much **numbness** have you had in your toes or feet **at its worst over the past 24 hours** (circle one number)?

0	1	2	3	4	5	6	7	8	9	10
None										As bad
										as can be

3. How much **numbness** have you had in your toes or feet **on average over the past 24 hours** (circle one number)?

0	1	2	3	4	5	6	7	8	9	10
None										As bad
										as can be

4. How much of a problem has **tingling** in your toes or feet been **in the past week**?

0	1	2	3	4	5	6	7	8	9	10
No tingling										Tingling in toes
in toes										and/or feet as
and/or feet										bad as you can
										imagine

5. How much **tingling** have you had in your toes or feet **at its worst over the past 24 hours** (circle one number)?

0	1	2	3	4	5	6	7	8	9	10
None										As bad
										as can be

6. How much **tingling** have you had in your toes or feet **on average over the past 24 hours** (circle one number)?

0	1	2	3	4	5	6	7	8	9	10
None										As bad
										as can be

7. How much of a problem has **pain** in your toes or feet been **in the past week**?

0	1	2	3	4	5	6	7	8	9	10
No pain in toes and/or feet										Pain in toes and/or feet as bad as you can imagine

8. How much **pain**, have you had in your toes or feet **at its worst over the past 24 hours** (circle one number)?

0	1	2	3	4	5	6	7	8	9	10
None										As bad as can be

9. How much **pain**, have you had in your toes or feet **on average over the past 24 hours** (circle one number)?

0	1	2	3	4	5	6	7	8	9	10
None										As bad as can be

10. Which is the most problematic symptom that you have now (**over the past day**)?

Numbness

[figure not shown]
Tingling

Burning/shooting pain

Other, please indicate _____

Appendix XIII Principals of Positioning and Titrating Scrambler Treatment

Algorithm 1: Basic Scrambler Treatment Algorithm

Algorithm 2: Advanced Scrambler Treatment Algorithm
(If patient does not meet criteria for proper electrode placement)

Option 1: Reduce Area of Pain

Place all electrodes above area of pain

- For feet, place electrodes on leg above area of pain, most likely minimum of 2 electrode sets, but may use as many as fit and are tolerated, or pain/tingling is zeroed
- For hands, place electrodes on arm above area of pain, most likely minimum of 2 electrode sets, but may use as many as fit and are tolerated, or pain/tingling is zeroed

Goal: Replace pain or tingling with new/different tingling sensation in the area of pain, in order to reduce area of pain/tingling and allow for proper placement of electrodes in next session

Treat for 30 minutes after tingling begins

* Patient assessed daily for ability to follow Algorithm 1

Option 2: Treat in area of pain

When electrode cannot be placed in area of non-pain, an electrode can be placed in the area of **least** pain and then Algorithm 1 can be followed

However, this can cause increased pain and discomfort and therefore this technique should be used based on provider experience and patient tolerability

Appendix XIVA Patient instruction form for using TENS on the upper extremities

1. You will be given a TENS machine, that you will be able to keep.
2. A nurse will provide hands-on instructions.
3. Before use, make sure that the TENS unit is charged.
4. Place a set of pads on the front and back of one wrist; then do the same thing on the other wrist with another set of pads.
5. Turn on the TENS machine.
6. Increase the intensity of the signal so that a signal is felt and it is comfortable..
7. Treat for a total of 30 minutes.

Appendix XIVB Patient instruction form for using TENS on the lower extremities

1. You will be given a TENS machine, that you will be able to keep.
2. A nurse will provide hands-on instructions.
3. Before use, make sure that the TENS unit is charged.
4. Place a set of pads below the ankle bone, inside and outside on one ankle; then do the same thing on the other ankle with another set of pads.
5. Turn on the TENS machine.
6. Increase the intensity of the signal so that a signal is felt and it is comfortable.
7. Treat for a total of 30 minutes.

Appendix XV Functional MRI (fMRI)

Data Analysis

Functional Data Analysis

Functional image data sets will be processed and analyzed using FSL (FMRIB's Software Library, www.fmrib.ox.ac.uk/fsl). Processing steps will include spatial filtering, high-pass temporal filtering, motion correction, geometric unwarping of EPI images, removal of all non-brain areas in images, and mean-based intensity normalization. Patients whose scans indicate head motion that exceeds 3mm will be excluded from the study.

Seed based connectivity analysis:

Functional connectivity will be measured using a seed correlation based approach (Fox, Snyder et al. 2005; Zhang, Snyder et al. 2008). For each subject, all brain time-courses will be orthogonalized to the eigen time-courses from WM and CSF extracted using a singular value decomposition (SVD)(Loan 1996) Correlation coefficients (CC) will be computed between the eigen time-course from the seed ROI and all other voxels in the brain. We will register the resulting statistical parametric maps from first-level analysis to the MNI 152 Brain (Montreal Neurological Institute) using FMRIBs Linear Image Registration Tool (FLIRT www.fmrib.ox.ac.uk/fsl). These registered CC maps will be transformed using a Fisher z-transform and entered into a mixed effects group analysis. The resulting z-statistic maps will be subjected to alternative hypothesis testing using Gaussian mixture modeling (GMM) for thresholding(Pendse, Borsook et al. 2009) with adaptive estimation of the null hypothesis.

Resting State Networks (RSN) using Independent Component Analysis (ICA):

The inherent run to run and inter data set variability of ICA will be captured by running ICA on independent data sets multiple times for each group. All ICA runs from each group will be entered into a RAICAR analysis(Yang, LaConte et al. 2008)to assess reproducibility of RSNs across runs and groups. We will compute p-values for reproducibility of each RSN using a non-parametric method. The matched ICA maps for significant RSNs from each subject group will be voxel-wise transformed to Normality followed by a mixed effects group analysis. The resulting statistical maps will be thresholded using mixture modeling that maximizes the model evidence.

Correlation Analysis:

We will carry out multivariate regression analysis across ROIs using (1) the estimated parameters for GLM and estimated sources in melodic results *versus* psychometric measures (e.g., depression scores, pain scores, anxiety levels); and (2) a fuzzy cluster analysis (FCA) that examines associations between ROIs using the psychometric measures and parameter estimates as features of interest.

Morphometric Analysis

Gray Matter Volume and Cortical Thickness: Gray Matter Volume: For cortical thickness, we will perform 2 MPRAGE scans in all subjects and average them for increased SNR. We will then construct and inflate hemisphere surfaces for the cortex based on the method defined by Dale and Fischl using Freesurfer (<http://surfer.nmr.mgh.harvard.edu/>) tools.(Dale, Fischl et al. 1999; Makris, Kaiser et al. 2006) This cortical mapping technique is described in an approach we have published in patients with trigeminal neuropathy(DaSilva, Becerra et al. 2008), opioid dependence(Upadhyay, Maleki et al. 2010) and migraine(Maleki, Becerra et al. 2011).

Article I. *Correlation with Functionally Defined ROI's:* We will perform the initial functional analysis of cortical areas activated during mechanical stimulation as noted above. Group statistical maps will be co-registered onto the reconstructed average surface brains of the subjects using Freesurfer. Using this surface-based approach, we can achieve precise cortical mapping and

measurements of cortical thickness leading to functionally defined ROIs identified during these chemical based experiments.

Correlation of disease frequency with Cortical Thickness: Changes in cortical thickness will be correlated with disease frequency and determine areas that seem to change with time. Other parameters, such as age, and disease duration will be regressed out.

Diffusion Tensor Imaging Analysis

Initially, we will correct all DTI datasets for eddy current distortion and head motion using FSL tools (Smith 2002). Fractional Anisotropic (FA) diffusion will be characterized on a voxel-wise basis by using a least squares fit of the tensor model to the DTI data in order to calculate the eigenvalues, λ_1 , λ_2 and λ_3 , and the eigenvectors e_1 , e_2 and e_3 of each DTI dataset and determine from them the fractional anisotropy (fa)(Pierpaoli and Basser 1996; Basser and Pierpaoli 1998) Fractional anisotropy maps will be registered to a standard brain using FSL's DTI tools. Group differences will be determined from aggregate results for each group (Upadhyay, Maleki et al. 2010).

Correlation analysis:

We will correlate observed changes in fractional anisotropy (FA) values with changes in RSN and various group characteristics and measures such as disease duration and frequency.

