Brain system adaptations in responders (greater than 50% pain or tingling reduction) vs. non-responders data will be provided from this work.

1.9b Sensation Changes

Our clinical experience with patients receiving Scrambler therapy has supported that patients develop improved normal sensation in areas treated with Scrambler therapy. This includes improved feeling and proprioception. Thus, we plan to look at quantitative sensory testing (QST) in a subset of patients on this trial. [name] and colleagues at Mayo have world-renowned expertise in this area. We will, in an exploratory manner, obtain touch pressure and heat pain testing on both the dorsal foot and the lateral leg in 10 patients per study arm, before Scrambler/TENS therapy and on the last couple days of ScramblerTENS therapy.

1.9c Audiovisual recording rationale

As Scrambler therapy is operator dependent and there is a learning curve with providing it, obtaining audiovisual recording of the treatment sessions should be helpful. This recording may allow us to ask for outside input for individual treatments that are being performed. It may also allow us to provide examples of successful treatment of individual patients. Of course, patient confidentiality issues need to be kept in mind.

We are proposing to include video recording of intervention delivery into the routine delivery of the intervention. Using established direction/observation protocols developed with local clinical communication research experts, we will consent patients to be video recorded.

[name], a co-investigator on this protocol, has extensive expertise with regard to patient communication topics, which have included audiovisual recording sessions of patient encounters. After the trial is completed this recordings may be used to conduct a structured "fidelity to treatment" analysis in which two independent raters score the recorded intervention delivery for fidelity to protocol a priori criteria based on scientific expert criteria. If we do this, raters will be blind to the final clinical outcomes of participants, although they would hear patients' thoughts while they were getting the treatments.

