 5. Beginning on Day 1 of active treatment and continuing for 14 consecutive days, complete Appendix V daily pre/post therapy. If no therapy is received on a day during this timeframe, complete once daily. To be filled out only for primarily treated area. For post-therapy questionnaires VIA and VIB.
 6. Prior to the last therapy.
 7. Appendix IX A or B, as labeled depending on pain or neuropathy area to be treated.
 8. If patient provides written consent for AV recording. Recording may be done on any day.
 9. Appendix XII A or B, as labeled depending on pain or neuropathy area to be treated.
 10. To be completed any time after completion of active treatment.
 11. Optional use in selected patients: Blood draws are completed at Baseline (prior to treatment) and on the last planned day or two of treatment (e.g., Day 9 or 10, if 10 treatments are given but sooner if earlier treatment completion is planned) (±2 days). Ideally, do prior to treatment. See [Section 14.0](#).
 12. fMRI: Optional use in selected patients, do at baseline and on approximately the last day of the initial treatment (±1 day).
 13. Quantitative sensory testing: Optional use in selected patients, do at baseline and then the last day of the initial treatment (±3 days) on 10 patients from each cohort. Do prior to treatment.
 14. For TENS patients only: Study Coordinator or Nurse to call on Treatment Day 2 and once on Treatment Day 8-10 to assess toxicities and remind the patient to complete daily questionnaires and mail them back.
- R Research funded

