7.3 Optional Substudies

7.31 Functional MRI (fMRI)

We plan to do fMRI on a subset of 12 patients, before Scrambler therapy and on the last planned day or two of treatment (± 1 day).

We will use the same approach have been used in the past for imaging experiments (Lebel, Becerra et al. 2008; Upadhyay, Knudsen et al. 2008; Upadhyay, Maleki et al. 2010). Subjects will be scanned on a HDxt 3.0T - 60cm TRM, Spectro (GE). During the MR session, subjects will be placed in the magnet for the experimental procedure and attached to various physiological monitoring apparatuses. During the experimental procedure, a series of standard anatomical images will be acquired. Once the anatomical images are completed, subjects will also undergo RSN (10 min), and DTI (10 min) imaging. The total estimated time the subject will be inside the magnet is 60 minutes. The imaging details are described below.

Anatomical Scans: We will use an established approach for imaging experiments. Subjects will be scanned on a 3.0T - 60cm TRM, Spectro (GE). We will acquire anatomical images using a magnetization prepared rapid gradient echo (MPRAGE) sequence (128 1.33mm-thick slices with an in-plane resolution of 1 mm (256x256)).

Resting State Scans (RSN): We will first obtain magnitude and phase images to unwarp functional scans; slice location, number, and thickness will be the same as those used in functional scans consisting of 41 slices with isotropic voxels (3mm) and 64x64 in-plane resolution. Then for RSN, we will generate images with a Gradient Echo EPI sequence (TR/TE = 2.5/30ms); 120 volumes will be collected per functional scan.

Diffusion Tensor Imaging (DTI): We will collect all DTI data using a single, shot-twice refocused echo planar pulse sequence at a 1.75 x 1.75 x 2.5 mm³ resolution. We will collect 8 single, non-diffusion weighted ($b = 0$ sec/mm²) volumes and 72, diffusion-weighted volumes with different gradient orientation at $b = 1000$ sec/mm² (TR = 7900 msec, TE = 92 msec, 5/8 partial Fourier, 3-fold SENSE acceleration). Fifty axial slices are sufficient to cover the entire cerebral cortex.

7.32 **mRNA blood testing**

mRNA blood testing will be done on a subset of 12 patients. Blood draws for CBC with differential and mRNA are completed at Baseline (prior to treatment) and on the last day or two of treatment (e.g., Day 9 or 10, if 10 treatments are given but sooner if earlier treatment completion is planned; ideally collected prior to treatment) (± 2 days).

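### Appendix XV's 3 mm head-motion rule should exclude scans from the fMRI analysis, not patients from the study, and the seed-based analysis should add motion parameters to its nuisance signals

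*Combined protocol and SAP*

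**What the plan says.** **Exclusion rule.** Under Functional Data Analysis, Appendix XV states: "Patients whose scans indicate head motion that exceeds 3mm will be excluded from the study". It does not say whether one bad scan of the two is enough.

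**Who is scanned, and when.** Section 7.31: "We plan to do fMRI on a subset of 12 patients, before Scrambler therapy", with a second scan near the end of treatment. Footnote 12 to the Section 4.0 schedule: "fMRI: Optional use in selected patients, do at baseline and on approximately the last day of the initial treatment". The footnote names no arm.

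**Motion handling.** Appendix XV: "Processing steps will include spatial filtering, high-pass temporal filtering, motion correction, geometric unwarping of EPI images". Before seed correlation, "all brain time-courses will be orthogonalized to the eigen time-courses from WM and CSF". No motion parameters, volume censoring or motion covariate is named.

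**Use of the results.** Section 1.9a2 promises data on "Brain system adaptations in responders (greater than 50% pain or tingling reduction) vs. non-responders". Section 16.36 says only that fMRI changes after Scrambler therapy will be described in the selected subset.

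**The concern.** The fMRI is an optional substudy inside a randomised comparison. A scan-quality rule should govern the imaging data set and nothing else. As worded, it removes the patient from the study, and the second scan falls after randomisation and treatment. Nothing elsewhere expressly limits the rule to the substudy, and Section 16 defines no analysis population that would override it. Section 16.6 does not replace patients whose primary data are missing. Section 16.5 will read a p-value below 0.05 on the primary endpoint as evidence that one therapy is better, so who is counted matters even in a trial described as not confirmatory.

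The second part concerns scans that pass the limit, which equals one functional voxel (3 mm isotropic in Section 7.31). Motion correction realigns the images but does not remove motion-related signal variance, and white-matter and CSF removal does so only in part. The planned contrasts are before versus after treatment and responders versus non-responders. If patients with less discomfort lie stiller, residual motion would follow those same contrasts.

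**Working it through.** **1. Does any section limit the exclusion?**
- The Schema gives adverse events and refusal as reasons for going off study.
- Sections 13.1 to 13.3 define ineligible, major violation and cancel. None mentions scan motion.
- Section 16.3 contains no imaging-based exclusion from the primary comparison, and no rule that scanned patients stay in it.

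The literal sentence is therefore neither confirmed nor cancelled elsewhere.

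**2. Exposure.** Inputs: 12 scanned (7.31), 50 patients at 25 per arm (16.5). 12/50 = 24%. If all 12 were Scrambler patients, 12/25 = 48% of that arm. These are the patients who could be affected, not expected losses.

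**3. Power under the literal reading.** The plan's own figures come first. Table 16.51 gives 80 to 82% power with 25 per arm at a one-sided 0.05 level. With the pooled-variance normal approximation,

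power = Φ{[(p2 − p1) − 1.645·√(p̄(1 − p̄)(1/n1 + 1/n2))] / √(p1(1 − p1)/n1 + p2(1 − p2)/n2)}.

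Row .10/.40, 25 per arm: (0.300 − 0.201)/0.115 = 0.858, so power is 80.4% (stated: 80). All five rows reproduce, at 80.7, 80.4, 81.7, 81.3 and 82.1%.

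The number lost is an assumption; the possible range is 0 to 12.

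| Assumed loss | TENS / Scrambler | Power over the five rows |
|---|---|---|
| none | 25 / 25 | 80.4–82.1% |
| 3 Scrambler | 25 / 22 | 78.4–79.6% |
| 6 Scrambler | 25 / 19 | 75.9–76.7% |
| 12 Scrambler | 25 / 13 | 67.2–70.5% |
| 6 per arm | 19 / 19 | 69.9–71.7% |

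**4. Bias if the loss is selective.** Assume 10 of 25 Scrambler patients respond and only non-responders are removed. The response rate moves from 10/25 = 40% to 10/22 = 45% (3 removed), 10/19 = 53% (6) or 10/13 = 77% (12, the extreme).

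**5. Residual motion, illustration only.** Suppose seed and voxel share no neural signal, and a fraction f of each one's variance is the same residual motion. Their correlation is then f. If f falls from 0.20 to 0.10 between scans, the Fisher z change is atanh(0.20) − atanh(0.10) = 0.2027 − 0.1003 = 0.102. These shares are assumed, and they must be what remains after motion correction and white-matter/CSF removal.

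- All 12 patients shift: t = 0.102/(SD/√12) = 3.5, 2.4 and 1.8 for an SD of the z change of 0.10, 0.15 and 0.20. The two-sided 5% limit is 2.20 (11 df).
- Only 6 responders shift and 6 non-responders do not: t = 0.102/(SD·√(1/6 + 1/6)) = 1.8, 1.2 and 0.9. The limit is 2.23 (10 df), and none reaches it.

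A simulation with 120 volumes per scan and the same shares gives a mean z change of −0.10 with SD 0.13, and a paired statistic of about −2.8 for 12 patients. If f falls only from 0.05 to 0, it gives −0.05 and about −1.3. The result depends on the assumed shares.

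**The case against.** The strongest reply is context. The sentence sits in an imaging appendix directly after the processing steps, and when the appendix later speaks of all subjects it can only mean those scanned. The rules on trial status lie elsewhere and omit scan motion, and Section 16.36 calls the fMRI a component of the study. This stands: the intended meaning is probably the fMRI analysis, and the defect is one of wording.

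A reader might infer that patients would be lost from the Scrambler arm alone. Goal 5 and Sections 7.31 and 16.36 do speak of Scrambler therapy. However, footnote 12 refers to selected patients without naming an arm, and the schedule marks the dermatome map as Scrambler-only but does not mark fMRI so. The arm mix is open.

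A reader might also infer that motion will make Hypothesis 5 look confirmed. The documents do not support that. The symptoms are in hands or feet, and no section links them to head motion. The hypothesis has no significance level or decision rule. The planned inference is a mixed-effects group analysis with mixture-model thresholding and an adaptively estimated null, which may absorb part of a diffuse shift. It is not a paired t-test.

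These replies limit the consequences. They do not supply the missing limit on the exclusion or the missing motion regressors.

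**Conclusion.** The point holds as two inexpensive corrections. First, the exclusion is worded for the whole study when it should cover only the imaging analysis. If followed literally, it could remove up to 12 of 50 randomised patients after randomisation, and power would fall to between 67 and 72% in the extreme cases computed. That rests on a literal reading that is probably not intended and on loss counts the documents do not give.

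Second, the seed-based analysis specifies no motion regressors. Residual motion can mimic a connectivity change only if it differs between scans or between the groups compared, which the documents neither show nor exclude. The t-values are illustrations under assumed motion shares and do not predict what this trial would find. The stake is limited to an exploratory, descriptive goal in an optional substudy.

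**What to change.** Replace the sentence in Appendix XV with: *Scans with head motion above 3 mm are excluded from the fMRI analysis only; the patient stays in the trial and in all other analyses.*

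In the seed-based analysis, add the six realignment parameters and their six derivatives to the white-matter and CSF nuisance set. Report mean frame-to-frame motion for each time point and by responder status, so that a reader can judge whether motion moved with the contrast of interest.

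The cost is one sentence and a few lines of text. The parameters come from the motion correction already planned. Twelve regressors use about 12 of the 120 volumes' degrees of freedom in each functional scan (10%). Nothing changes in recruitment, scanning or the primary analysis.
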